7.1. Definitions

- Baseline is synonymous with screening, and the baseline value (or baseline result) is that measured during the screening visit prior to the first administration of BIO 300 Oral Powder.
- Day 1 is the first day of dosing with BIO 300 Oral Powder.
- Estimand is the estimated value for a parameter or, alternatively, a formula and/or description for how a parameter is estimated.
- Proportional months, defined for durations of time reported in months, are given by the formula

$$\text{months} = \frac{12}{365.25} \times \text{days}$$

- Shift table is a two-way frequency table pairing baseline value with the most extreme post-baseline result.

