8.2 SAFETY AND OTHER ASSESSMENTS

Physical Exam – Examination of the participant’s cardiovascular, HEENT, lymphatic, pulmonary, gastrointestinal, musculoskeletal, and neurological systems.

Vital Signs – Vital signs will record the patient’s height, weight and BMI. They will also measure heart rate, blood pressure (systolic and diastolic), respiratory rate, and body temperature.

Electrocardiogram – ECGs occur during the screening visit, on visit 2 (1 hr before, 1hr after, 2 hrs after and 4 hrs after BIO 300 Oral Powder dose), and visits 3-5 for the SAD phase. ECGs will occur during the screening visit, visit 2 (1 hr before, 1hr after, 2 hrs after and 4 hrs after BIO 300 Oral Powder dose), visits 3-4, visit 7 and visit 10 for the multiple single dose phase. ECGs will be digitally read locally at the study site. ECGs will be completed in triplicate and the average will be used to determine if the study subject has an abnormal reading.

QTc Interval Prolongation – Fridericia-corrected QTc (QTcF) interval from all subjects in both the SAD and the multiple single dose studies will be used to evaluate QTcF interval prolongation. QTcF prolongation will be determined by evaluating ECG at baseline (pre-dose) and at multiple time points around the predicted C_{max} of BIO 300 Oral Powder (ECG timepoints listed above). QTcF intervals will be reported for each dosing cohort as a mean and standard deviation. The upper limit for QTcF interval prolongation will be >480 ms or absolute QTcF change from baseline of >30 ms with a 95% confidence interval. The relationship between drug exposure and mean QTcF interval change will be evaluated in the SAD study using both C_{max} and AUC. Any adverse events that may signal a potential proarrhythmic effect will be carefully monitored (e.g., Torsade de pointes, sudden death, ventricular tachycardia, seizures, etc.).

Complete Blood Count – Blood sampling for the laboratory parameters will be performed during the screening and BIO 300 Oral Powder treatment period according to the study schedule (**Section 1.3**). A complete blood count with differential will evaluate hemoglobin, hematocrit, red blood cells (RBCs), white blood cells (WBCs), neutrophils, lymphocytes, monocytes, eosinophils, basophils, and platelet count.

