9 STATISTICAL CONSIDERATIONS

9.1 STATISTICAL HYPOTHESES

Data analysis of the primary endpoints will be based on measurements of genistein aglycone (free genistein) serum concentrations (0-48 h). They will also be based on safety assessments which include blood counts, serum chemistries, urinalysis, ECGs, vital signs, and PTT/INR at the timepoints listed in the **SoA, Section 1.3**. “Baseline” will refer to measurements taken during the screening visit. If no “baseline” data exists from a parameter, then changes in the parameter time regression will be compared.

As this is a single dose escalation and multiple single dose trial evaluating the safety and pharmacokinetic profile of BIO 300 Oral Powder, the statistical hypotheses for the safety measurements is that there will be no change in safety measurements during BIO 300 Oral Powder dosing, and 7 days after the last BIO 300 Oral Powder dose.

For the secondary endpoint, the statistical hypothesis is that there will be a significant change in the level of expression of one or more genes that is attributable to BIO 300 Oral Powder dose.

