9.4 STATISTICAL ANALYSES

9.4.1 GENERAL APPROACH

An independent statistician using standard statistical techniques will determine statistically significant differences in the trial measurement data. Statistical significance will be set at the nominal level of $p<0.05$. Plasma concentrations (genistein aglycone; free genistein) will be measured (AUC, C_{max} , T_{max} , $T_{1/2}$) and plasma kinetic rate will be calculated using standard procedures and statistical analyses (e.g., AUC using the linear trapezoidal formula and $T_{1/2}$ using linear regression). Data will be summarized by descriptive statistics (mean/medians and standard errors/confidence intervals for continuous response variables and distribution tables or histograms for discrete response variables).

Baseline characteristics will be compared using matched-pair t-tests. The computed change from baseline will be calculated for all measured variables and expressed as the mean change from baseline

and accompanying standard deviation (SD) of the change from baseline. Repeated measures ANOVA tests will be used to compare changes in scores for each variable between each treatment group. Matched pair t-tests will be used to compare the change scores within each treatment group. All data analyses will be conducted on the subjects who completed the study treatment periods and statistical significance will be set at $p<0.05$.

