9.4.2 ANALYSIS OF THE PRIMARY EFFICACY ENDPOINT(S)

Blood counts, serum chemistry, urinalysis, ECGs, vital signs, and PTT/INR for the study cohorts will be reported as a mean \pm SD at each of the timepoints listed in the **SoA, Section 1.3**. An analysis of covariance (ANCOVA) to compare the cohorts after adjusting for "baseline" (the adjustment covariate) will be completed. Analysis will be performed in individual subjects to identify changes in safety measurements relative to baseline, and between cohorts at the timepoints listed in the **SoA, Section 1.3** to identify any potential dose-response relationships.

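### QTcF change has two conflicting baselines (screening and Day 1 pre-dose), and the RNA analysis relative to baseline has no usable or named reference sample

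*Combined protocol and SAP*

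**What the plan says.** **General rule.** SAP 7.1: "Baseline is synonymous with screening, and the baseline value (or baseline result) is that measured during the screening visit". The sentence goes on to require that the value precede the first dose. Protocol 9.1 says that the term "will refer to measurements taken during the screening visit", and adds that for a parameter with no such data "changes in the parameter time regression will be compared". Protocol 9.4.1 sets the scope: "The computed change from baseline will be calculated for all measured variables and expressed as the mean change from baseline". SAP 7 has the same rule, with an ANCOVA of change that uses baseline as covariate.

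**QTcF.** Protocol 8.2 uses a different reference: "QTcF prolongation will be determined by evaluating ECG at baseline (pre-dose", where the bracket closes. Part of its limit for prolongation is an "absolute QTcF change from baseline of >30 ms with a 95% confidence interval". Note 9 of the Schedule of Activities places an ECG within 1 h before the Day 1 dose, in addition to the screening ECG. Protocol 9.4.2 lists ECGs among the variables concerned: "Blood counts, serum chemistry, urinalysis, ECGs, vital signs, and PTT/INR for the study cohorts will be reported". It then plans "An analysis of covariance (ANCOVA) to compare the cohorts after adjusting for" baseline, the term that 9.1 ties to screening. SAP 10.5 plans descriptive QTc statistics by time relative to dosing and says nothing about the reference for a change.

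**RNA.** Protocol 9.4.3 seeks differentially expressed genes in individual subjects relative to baseline. The schedule, the visit descriptions in protocol 8.3 and the blood-volume tables in 8.3.1 and 8.3.2 show no RNA draw at screening. SAP 9.3 compares groups of samples with DESeq2 without defining the groups.

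**PK.** SAP 9.2 names the pre-dose sample as time zero.

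**The concern.** A programmer who follows SAP 7 and 7.1 computes QTcF change from an ECG taken 8 to 28 days before dosing. A reader of protocol 8.2 expects change from the ECG taken within the hour before dosing. The result is compared with a 30 ms limit and related to Cmax and AUC, so the two readings can give different answers to a stated safety question. The conflict also lies inside the protocol (8.2 against 9.1 and 9.4.2), so giving the protocol precedence over the SAP does not remove it.

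For the RNA endpoint the screening rule points to a sample that does not exist. The within-subject reference would then be settled by whoever runs the analysis, in an open-label study and possibly after data have been seen.

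**Working it through.** **1. References for a QTcF change, side by side**

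| Source | Reference |
|---|---|
| SAP 7.1, applied to all variables by SAP 7 | Screening visit |
| Protocol 9.1, used by 9.4.1 and 9.4.2 | Screening visit |
| Protocol 8.2, QTc paragraph | Pre-dose ECG |
| SAP 10.5 | Not stated |

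Both ECGs exist for every subject, so both versions can be computed.

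**2. How far the versions differ**

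Let P(t) be a subject's QTcF at time t after dosing, S the screening value and D the mean of the Day 1 pre-dose triplicate.

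(P(t) − S) − (P(t) − D) = D − S

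The difference does not depend on t. If the change from pre-dose is c, the change from screening is c + (D − S), and the versions disagree on the limit when 30 ms lies between these two numbers. A cohort mean change shifts by the cohort mean of D − S. The documents give neither the mean nor the spread of D − S. If it is zero in every subject, the choice does not matter. The other part of the limit, an absolute QTcF above 480 ms, needs no baseline.

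**3. How many values are affected**

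Inputs: at least 24 SAD and 8 MSD completers (protocol 9.2); ECG times from the schedule and protocol 8.2.

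- SAD: Day 1 at 1, 2 and 4 h, plus Days 2, 3 and 8 = 6 per subject; 24 × 6 = 144.
- MSD: Day 1 at 1, 2 and 4 h, plus Days 2, 3, 6 and 13 = 7 per subject; 8 × 7 = 56.
- Total: 144 + 56 = 200.

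Protocol 8.2 speaks of times around the predicted Cmax. If that means only the Day 1 ECGs with a stated time after dosing, the count is 32 × 3 = 96.

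**4. RNA draws at screening**

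The plan's own volumes are reproduced with no screening draw:

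- SAD: 5 mL × 4 (Day 1) + 5 mL (Day 2) = 25 mL, as in 8.3.1.
- MSD: 5 mL × 4 (Day 1) + 5 mL × 4 (Day 6) + 5 mL (Day 7) = 45 mL, as in 8.3.2.

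That is 5 samples per SAD subject and 9 per MSD subject: 24 × 5 + 8 × 9 = 192 in all. None is from screening, and 32 (one per subject, Day 1 pre-dose) are untreated.

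**5. Can the text supply an RNA reference?**

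- The protocol 9.1 fallback compares time regressions. It names no sample and does not yield genes expressed differently relative to baseline.
- SAP 7.1 has no fallback.
- SAP 9.3 neither mentions baseline nor says which samples form its groups.
- The Day 1 pre-dose sample is the only untreated one. In the MSD cohort the Day 6 pre-dose sample follows five daily doses (Days 1 to 5), so it fails the SAP 7.1 condition that baseline precede the first dose.

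The RNA gap is therefore one of designation, not of data.

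**The case against.** The strongest reply is that specific text governs general text. SAP 9.2 uses pre-dose for PK despite 7.1, so protocol 8.2 may be read as doing the same for QTcF, and SAP 10.5 is descriptive, with full listings from which either change can be recomputed. This makes the likely intention clear and means that nothing is lost. It does not settle the matter. The SAP departs from 7.1 explicitly for PK and not for ECG, and protocol 9.4.2 still puts ECGs in a comparison adjusted for the screening value.

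On RNA, protocol 9.1 places its definition in a paragraph on the primary endpoints, so it may not be meant for RNA, and the Day 1 pre-dose sample is the natural choice. Both points stand. What is missing is the sentence that says so, while SAP 7.1 carries no such limit of scope.

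Three stronger readings are tempting and are not supported:

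- *That the Day 6 pre-dose sample is a rival baseline in the MSD cohort.* The first-dose clause in SAP 7.1 excludes it, and no section calls it baseline.
- *That SAP 7.1 leaves a counted set of SAP RNA contrasts without a baseline.* The relative-to-baseline wording is in protocol 9.4.3. SAP 9.3 does not use the term, and its fault is undefined groups.
- *That the vital-sign baseline is also wrong.* The documents agree on screening there, so moving it would be a preference.

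**Conclusion.** The point holds for QTcF and RNA. QTcF change has two contradictory references, affecting up to 200 values at the minimum numbers of completers, or 96 on the narrow reading of protocol 8.2. Its effect equals pre-dose minus screening in each subject; the documents do not give that size and it may be nil, so no rate of wrongly flagged subjects is claimed. For RNA, the requested comparison relative to baseline has no screening sample behind it and no other reference named, although a suitable sample is collected.

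The counts assume 24 SAD and 8 MSD completers with every scheduled ECG and RNA sample obtained. A reader might infer that dose escalation is at risk. It is not on the documents' terms, because protocol 7.5 bases escalation on counts of dose-limiting toxicities. Sample size and alpha are unaffected too. This should be fixed: following the rule as written contradicts the protocol's own QTcF criterion and cannot be carried out for RNA.

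**What to change.** In SAP 7.1 and protocol 9.1, keep screening as the general definition and add two exceptions:

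- **ECG/QTcF:** baseline is the mean of the Day 1 pre-dose triplicate, in line with protocol 8.2. State in SAP 10.5 that QTcF change uses it. Through the revised 9.1 definition, the ECG comparison in protocol 9.4.2 then uses the same value.
- **RNA:** the Day 1 pre-dose sample is the within-subject reference for all later samples, including MSD Days 6 and 7. Name it in SAP 9.3 and define there the groups to be compared.

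Leave screening as baseline for the laboratory tests and vital signs, and PK time zero as in SAP 9.2.

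The cost is a few sentences in SAP 7.1, 9.3 and 10.5 and in protocol 9.1. Every measurement needed is already scheduled. The protocol history shows that version 2.0 drew on Cmax from all four SAD cohorts, so the change should be dated and recorded as a clarification made after those data were available.

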7.2. Missing Values

Given the small sample size, descriptive statistics and other analyses will be completed without replacing or imputing missing values.

7.3. Visit Windows

The study protocol defines a visit schedule based on the number of days since the first dose of BIO 300 Oral Powder (Day 1). All study participants will be instructed on when they need to return to the clinic in order to meet all scheduled assessments. Assessments outside of the scheduled visit window will be analyzed (by visit according to the clinical database) as if they occur within the visit window; that is, no data will be excluded if it is measured outside the visit window.

7.4. Interim Analysis

Following the third SAD cohort, PK analysis will be completed for all subjects (cohorts 1-3) and analyzed along with all safety data to determine the dose for the final cohort of the SAD study. No other interim analyses are planned. SMC data reviews are not considered interim analyses (see **Section 6**).

7.5. Significance level

An independent statistician using standard statistical techniques will determine statistically significant differences in the trial measurement data at the nominal 0.05 level of significance.

8. General Data Analyses

8.1. Subject Disposition

The numbers of subjects who were enrolled and dosed with BIO 300 Oral Powder will be summarized by frequency counts. Reasons for discontinuing BIO 300 Oral Powder and study completion status will be summarized as categorical variables (number and percentage of subjects in each category). Relevant data supporting these summaries will be listed by subject.

8.2. Protocol Deviations

Study inclusion/exclusion criteria violations and protocol deviations recorded in the clinical database, if any, will be summarized as categorical variables (number and percentage of subjects in each category). Relevant data supporting this summary will be listed by subject.

8.3. Baseline and Demographic Characteristics

Demographic and baseline characteristic data will be summarized with descriptive statistics for age, gender, race, ethnicity, height, weight, BMI, vital signs and laboratory results. ANOVA analysis will be used to compare each parameter between the study cohorts at baseline.

9. Endpoint Analyses

All observations available in the study database will be included in endpoint analysis regardless of subjects' aggregate exposure to BIO 300 Oral Powder, use of concomitant medications, or violations of the protocol. Relevant data supporting efficacy analyses will be listed by subject.

9.1. Analysis for Safety Endpoints

Safety data will include adverse events (AEs), safety laboratory (CBC/hematology, serum chemistry and urinalysis), pregnancy (if applicable), drug and alcohol tests test, physical exam, ECG, and vital signs. The proportion of subjects experiencing adverse events, serious adverse events, and DLTs will be summarized for each dosing cohort. See **Section 10** for more information on safety analysis.

9.2. Analysis for the Pharmacokinetic Profile

PK parameters will be estimated using nominal sampling times relative to each dose administration and nominal doses unless otherwise specified. Serum concentration values obtained at the predose time point will be used to estimate the concentration at time zero (baseline). Concentration values reported as not quantifiable (BLQ, <1.0 ng/mL) will be assigned a value of zero.

The area under the concentration vs. time curve (AUC) will be calculated using the linear trapezoidal method with linear interpolation. The AUC will not be calculated for PK profiles with less than 3 quantifiable concentrations of BIO 300 Oral Powder at separate time points. When practical, the terminal

elimination phase of each concentration versus time curve will be identified using at least three observed concentration values after Cmax, but not including Cmax. The slope of the terminal elimination phase will be determined using log linear regression on the unweighted concentration data. Parameters relying on the determination of the terminal elimination phase will not be reported if the coefficient of determination is less than 0.800, or if the extrapolation of the AUC to infinity represented more than 20% of the total area. The parameters Tmax, Cmax, AUC(0-t), AUC(0-inf) and T1/2 will be reported for each SAD cohort and for the MSD cohort on after the Day 6 dose of BIO 300 Oral Powder.

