8. Vital signs to be obtained within 1 hour prior to administration of BIO 300 Oral Powder and then approximately 30 minutes, 1, 2, 4, 6, 8, and 12 h following administration of BIO 300 Oral Powder
9. ECGs to be obtained within 1 h prior to BIO 300 Oral Powder administration and then approximately 1, 2, and 4 h following BIO 300 Oral Powder administration
10. Samples for PK assessment to be obtained just prior to BIO 300 Oral Powder administration and then 30 minutes, 1, 2, 4, 6, 8, and 12 h following BIO 300 Oral Powder administration. The time of the blood draw will be ± 10 minutes of the nominal time.
11. Samples for PK assessment to be obtained 24 ± 2 h following administration of BIO 300 Oral Powder
12. Samples for PK assessment to be obtained 48 ± 4 h following administration of BIO 300 Oral Powder
13. Samples for PK assessment to be obtained just prior to administration of BIO 300 Oral Powder and then 30 minutes, 1, 2, and 4 h following BIO 300 Oral Powder administration. The time of the blood draw will be ± 10 minutes of the nominal time.
14. Samples for PD assessment to be obtained -2 to 0 h before BIO 300 Oral Powder administration, and 1, 2, and 4 h following BIO 300 Oral Powder administration. The time of the blood draw will be ± 10 minutes of the nominal time.
15. Samples for PD assessment to be obtained 24 ± 2 h following administration of BIO 300 Oral Powder
16. Samples for PD assessment to be -2 to 0 h before BIO 300 Oral Powder administration, and 4, 8, and 12 h following BIO 300 Oral Powder administration. The time of the blood draw will be ± 10 minutes of the nominal time.
17. Vital signs to be obtained within 1 hour prior to administration of BIO 300 Oral Powder and then approximately 30 minutes, 1, 2, and 4 h following administration of BIO 300 Oral Powder

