All subjects will have their blood collected for serum as described above. Serum samples will be collected for pharmacokinetics just prior to and following administration of a single dose of BIO 300 Oral Powder at 30 minutes, 1, 2, 4, 6, 8, and 12 hours. The time of the blood draw will be ± 10 minutes of the nominal time. Subjects will be given a standardized low-soy meal after the 4 h blood draw and 2 h after the 6 h blood draw. Whole blood will be collected as described above for RNA isolation prior to a single dose BIO 300 Oral Powder administration, and at 1, 2 and 4 hours after administration.

Visit 3 (Day 2)

All subjects will have blood serum collected for PK 24 ± 2 hrs after BIO 300 Oral Powder dosing. Whole blood will also be collected for RNA isolation 24 ± 2 hrs after BIO 300 Oral Powder dosing.

Visit 4 (Day 3)

All subjects will have a whole blood and serum collected for CBC, PT/INR, PTT, 48 ± 4 hrs PK and serum chemistry as described above.

Visit 5 (Day 8)

All subjects will have a whole blood and serum collected for CBC, PT/INR, PTT and serum chemistry as described above.

Multiple Single Dose

Visit 1 (Screening)

At the screening visit, blood will be collected to acquire the subject's baseline blood counts, serum chemistries, PT/INR, PPT, and viral testing. If a pregnancy test is required for the subject, either a serum or urine test will be done at this time. These test results will assist in determining the subject's ability to be included in the trial (see **Section 5.1 Inclusion Criteria**).

Visit 2 (Day 1)

All subjects will have their blood collected for serum as described above. Serum samples will be collected for pharmacokinetics just prior to and following administration of a single dose of BIO 300 Oral Powder at 30 minutes, 1, 2 and 4 hours. The time of the blood draw will be ± 10 minutes of the nominal time. Whole blood will be collected as described above for RNA extraction prior to a single dose BIO 300 Oral Powder administration, and at 1, 2 and 4 hours after administration.

Visit 4 (Day 3)

All subjects will have a whole blood and serum collected for CBC, serum chemistry, and PT/INR, PPT as described above.

Visit 5 and 6 (Days 4 and 5)

All volunteers will have their vital signs performed and will be administer a single dose of BIO 300 Oral Powder at the research unit.

Visit 7 (Day 6)

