All subjects will have their blood collected for serum as described above. Serum samples will be collected for pharmacokinetics just prior to and following administration of a single dose of BIO 300 Oral Powder at 30 minutes, 1, 2, 4, 6, 8, and 12 hours. The time of the blood draw will be ± 10 minutes of the nominal time. Subjects will be given a standardized low-soy meal after the 4 hr blood draw and 2 hours after the 6-hour blood draw. Serum will also be used for serum chemistry analysis. Whole blood will be collected as described above for RNA extraction prior to a single dose BIO 300 Oral Powder administration, and at 4, 8 and 12 hours after administration. Whole blood will also be collected for CBC analysis.

Visit 8 (Day 7)

All subjects will have blood serum collected for PK 24 ± 2 hrs after BIO 300 Oral Powder dosing. Whole blood will also be collected for RNA extraction 24 ± 2 hrs after BIO 300 Oral Powder dosing.

Visit 9 (Day 8)

All subjects will have blood serum collected for PK 48 ± 4 hrs after BIO 300 Oral Powder dosing.

Visit 10 (Day 13)

All subjects will have a whole blood and serum collected for CBC, serum chemistry, and PT/INR, PPT as described above.

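### PK parameters are computed from nominal times although the 24 h and 48 h draws may move by 2 h and 4 h; actual times are a cheap, small improvement

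*Combined protocol and SAP*

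**What the plan says.** SAP 9.2 sets the time basis: "PK parameters will be estimated using nominal sampling times relative to each dose administration and nominal doses unless otherwise specified". No other section specifies otherwise for PK.

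The Schedule of Activities (protocol 1.3) holds draws up to 12 h to ±10 minutes but is looser afterwards. Note 11 reads "Samples for PK assessment to be obtained 24 ± 2 h following administration of BIO 300 Oral Powder" and note 12 reads "Samples for PK assessment to be obtained 48 ± 4 h following administration of BIO 300 Oral Powder". Protocol 8.3 repeats the 48 h window for the single-dose cohorts ("48 ± 4 hrs PK and serum chemistry as described above") and after the Day 6 dose ("All subjects will have blood serum collected for PK 48 ± 4 hrs after BIO 300 Oral Powder dosing").

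Under SAP 9.2 the terminal phase is "identified using at least three observed concentration values after Cmax, but not including Cmax", and its slope comes from log-linear regression. Parameters that depend on it are suppressed if R² is below 0.800 or "if the extrapolation of the AUC to infinity represented more than 20% of the total area". On low values: "Concentration values reported as not quantifiable (BLQ, <1.0 ng/mL) will be assigned a value of zero". A zero cannot enter a log regression, so the last quantifiable draw ends the fit. T1/2, AUC(0-t) and AUC(0-inf) are reported for each single-dose cohort and after Day 6. AUC(0-24) and AUC(0-48) appear in protocol 8.1.

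SAP 7.3 keeps out-of-window assessments and analyses them as on time, without saying whether that covers PK sample times. Protocol 7.4 treats a missed visit with timed PK draws as loss to follow-up, but does not address an early or late draw.

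**The concern.** The widest windows fall on the latest samples, which have the most leverage on a terminal slope, and that slope may rest on only three points. A sample drawn at 44 h but analysed as 48 h looks too high for its assigned time, so T1/2 comes out too long; a late draw does the reverse. The PK profile is part of the primary objective and the cohorts have only 6 to 8 planned completers. The analysis itself creates this error, and it can be removed without a new sample.

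**Working it through.** The documents give no half-life, concentration level, draw-time distribution or T1/2 precision, so there is no stated figure to reproduce. What follows is conditional on the assumptions shown.

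**Inputs from the documents.** Post-dose sampling at 0.5, 1, 2, 4, 6, 8, 12, 24 and 48 h; windows w of ±10 min up to 12 h, ±2 h at 24 h, ±4 h at 48 h; log-linear fit on at least three points after Cmax.

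**Assumed.** A mono-exponential terminal phase; timing errors e independent and uniform over the window, or over half of it for the two late draws.

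**Formula.** With weights c_i = (t_i - t̄)/Sxx, the slope fitted on nominal times is -λ(1 + Σc_i e_i). The relative T1/2 error is 1/(1 + Σc_i e_i) - 1. It does not depend on the true half-life, and its SD is approximately √(Σ c_i² w_i²/3).

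**Fit on 12/24/48 h.** t̄ = 28 and Sxx = 256 + 16 + 400 = 672, so c = -0.0238, -0.0060, 0.0298.
- 48 h term: 0.0298 × 4/√3 = 0.0687
- 24 h term: 0.0060 × 2/√3 = 0.0069
- 12 h term: 0.0238 × (1/6)/√3 = 0.0023

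The root sum of squares is 6.9%, nearly all from the 48 h window.

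**Fit on 8/12/24 h.** t̄ = 14.67 and Sxx = 138.67, so c = -0.0481, -0.0192, 0.0673. The 24 h term is 0.0673 × 2/√3 = 0.0777, and the total is 7.8%.

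| Fit | SD, full windows | SD, half windows |
|---|---|---|
| 8/12/24 h | 7.8% | 3.9% |
| 6-24 h | 6.8% | 3.4% |
| 12/24/48 h | 6.9% | 3.5% |
| 6-48 h | 5.5% | 2.7% |
| 4-48 h | 5.1% | 2.6% |

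Simulation agrees to about 0.1 point. Mean bias is below 1% when timing is balanced. Seven-point fits fall slightly lower, at about 4.9% and 2.4%.

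**Consistently early or late draws.** For 8/12/24 h with every 24 h draw 2 h early, Σce = -0.1346 and the error is 1/0.8654 - 1 = +15.6%; 2 h late gives 1/1.1346 - 1 = -11.9%. For 12/24/48 h with both late draws at the same edge, Σce = ±0.107, giving +12.0% (early) and -9.7% (late).

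**Cohort summaries.** With between-subject CV v and timing SD s, the standard error of the mean is inflated by √(v² + s² + v²s²)/v - 1. At an assumed v of 30%, s = 2.57% gives 0.4% and s = 7.9% gives 3.7%. Over v of 20-50% the range is about 0.2% to 8%.

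**When 12 h is last.** The 6/8/12 h fit has a timing SD of 2.2%. With an assumed 10% assay CV, total T1/2 SD is 6.6-12.5% on nominal times and 6.8-12.3% on actual times, so nothing is gained. Whether 48 h enters the fit depends on level. With the 1.0 ng/mL limit it needs a Cmax of about 87-203 ng/mL at a 6 h half-life, but only 9-14 ng/mL at 12 h.

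**AUC(0-48), 48 h quantifiable** (one-compartment profiles, half-life 6-16 h, absorption rate 0.5-2/h, all assumed). The SD is 1.8-2.3% on nominal times and 0.6-0.9% on actual times taken to a fixed 48 h limit. Running to the actual last draw instead is worse than nominal at a 16 h half-life: 2.0-2.2% against 1.8-1.9%.

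**48 h sample below the limit** (half-life 4-8 h). The trapezoid to zero at 48 h exceeds extrapolation with the fitted slope by 1.8-3.6%. That is as large as the error being removed, so the wording must say which rule applies.

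**The case against.** The strongest reply is that little depends on this. Nominal times are prespecified and simple, and the study is mainly descriptive. Escalation rests on dose-limiting toxicities (protocol 7.5). The PK review before cohort 4 (protocol 9.4.6, SAP 7.4) states no T1/2 criterion. Between-subject spread dominates cohort summaries. All of this stands, and it keeps the point minor.

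Feasibility is a fair objection too. The amendment history (protocol 10.3) shows that all four single-dose cohorts had been sampled by version 2.0. The documents do not say that dose and draw clock times were kept. A fallback to nominal times would mix time bases between subjects and could differ from the interim PK results.

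Three stronger readings are tempting, and the documents support none of them. A reader might infer that the reported half-lives will be biased. That needs draws to run consistently one way, and nothing indicates that they do. Nor do the documents show that timing is balanced, so the error cannot be called purely random. A reader might infer that a dose decision is at risk, but no stated rule uses T1/2. A reader might also take 5-8% as the expected error. It is conditional on uniform timing over the full window and on a quantifiable 24 h or 48 h draw ending the fit.

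**Conclusion.** The point holds as a minor, inexpensive improvement. The per-subject error and its possible cohort-level shift are real where a 24 h or 48 h draw ends the fit, and actual times remove both forms almost completely under a mono-exponential terminal phase. The case for changing is that the error is avoidable, not that it threatens a conclusion. The ±2 h and ±4 h limits bound the error only if draws stay inside them, and SAP 7.3 leaves that open for PK. Half-life, concentration level, draw-time distribution and between-subject CV are all assumptions here.

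**What to change.** In SAP 9.2, state that:
- the terminal slope, T1/2 and AUC use actual elapsed time since the actual dose, and dose and draw clock times are recorded;
- nominal times are used for concentration summary tables and plots, and where an actual time is missing; those subjects are listed, because time bases are then mixed;
- AUC(0-t) ends at the fixed nominal time of the last quantifiable sample, reached by interpolation if that draw was late or by the fitted terminal slope if it was early; where the slope is not reportable, that draw takes its nominal time;
- for AUC(0-24) or AUC(0-48) with a sample at the limit below 1.0 ng/mL, the existing zero rule applies at the nominal time, with no slope extrapolation.

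In SAP 7.3, state that visit slotting does not apply to PK sample times.

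The cost is a few sentences and a little programming, with no new samples. The linear trapezoid remains, except for the short fitted segment after an early last draw. The downside is reliance on recorded clock times. For the single-dose cohorts already sampled by version 2.0, the change works only where those times exist.
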